Computer-based cognitive training programs provide a safe, tolerable tool to reduce VAN reactivity and potentially treat pediatric anxiety disorders. Randomized controlled trials already support the use of cognitive training programs with targets different from the VAN. 20-22 For example, attention bias modification (ABM) trains individuals to ignore threatening stimuli in order to improve symptoms of anxiety. While promising, this treatment generates no more than modest effects on symptoms. The treatment in this study was specifically designed to reduce reactivity of the overactive VAN associated with pediatric anxiety disorders, by training individuals to actively ignore salient stimuli while maintaining attention on a particular task. By targeting a particular brain network that implements a core psychological process disrupted early in the developmental pathway to anxiety disorders, this novel treatment could represent a major improvement to current cognitive training approaches and may have a more substantial impact on symptoms.

B2 Rationale for this Study

Previous findings support the hypothesis of an overactive VAN in pediatric anxiety disorders and suggest that reducing VAN reactivity may have a specific effect in reducing anxiety symptoms. Yet, no treatments have been developed to explicitly correct VAN dysfunction by directly targeting this network. The treatment studied in this project aims to fill that gap. The rationale of this research is that it could lead to a novel, safe, mechanism-based treatment for a major public health problem.

C Study Objectives

C1 Primary Aim

Test the efficacy of a novel computer-based cognitive training program in the treatment of pediatric anxiety disorders using a pilot double-blind, randomized, placebo-controlled

design. The primary outcome will be reduction in symptoms of anxiety as measured by the Pediatric Rating Scale (PARS).

C2 Secondary Aim

Uncover the neural effects of the cognitive training program using functional magnetic resonance imaging (fMRI).

C3 Rationale for the Selection of Outcome Measures

The PARS is a clinician-administered measure of pediatric anxiety that incorporates both parent and child report.²⁶ Because it includes multiple informants and is anchored by a clinician, it has high reliability and validity and is widely used.

D Investigational Agent

D1 Preclinical Data

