This is the first study to use this exact computer training regimen for testing in its ability to reduce symptoms of anxiety in children with anxiety disorders. Each session of the computer game takes approximately 30 minutes and subjects complete 8 total sessions over one month. The computer game involves paying attention to parts of the screen while distracting square boxes appear at other locations. A target "X" appears at the location that participants are paying attention to and the subjects press a button when it appears. We have piloted this protocol in 4 healthy children between the ages of 7 and 17 years of age. The procedure was well tolerated with no adverse events reported in any of the subjects.

D2 Clinical Data to Date

There are no clinical data to date on this computer training program. Other cognitive training programs such as attention bias modification that involve similar procedures have proven effective for treating anxiety disorders in meta-analyses with no known adverse events reported.

D3 Dose Rationale and Risk/Benefits

The dose is based on dosing of computer-based cognitive training programs in the literature. We will have subjects complete between 250 and 300 trials of the training program (30 minutes total) for each session; subjects complete 8 total training sessions.

Potential benefits are reduced anxiety and improved attentional control.

There are no known significant risks to this treatment. Potential mild risks include boredom, fatique, and slight stiffness from sitting in a chair for 30 minutes.

E Study Design

E1 Overview or Design Summary

The study consists of a Baseline Psychiatric Assessment, Baseline Neuroimaging Assessment, Cognitive Training, Follow-up Psychiatric Assessment, and Follow-up Neuroimaging Assessment.

Baseline Psychiatric Assessment: Subjects and their primary caregiver undergo a psychiatric interview (regarding the child) and answer questions regarding recent symptoms. Children also complete 3 different computer games (taking between 60 and 90 minutes total). These computer games are designed to measure stimulus-driven attention, attention bias to threat, and attentional control.

Baseline Neuroimaging Assessment: Subjects undergo fMRI while they perform a task that measures their stimulus-driven attention and attention bias to threat.

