Children will be recruited through local schools, pediatricians' offices, and through [name] child anxiety clinic by asking staff to present IRB approved recruitment materials to potentially interested families. We will also recruit with advertisements, press releases, websites, and placement of approved flyers and materials throughout the greater Washington University community as well as throughout the St. Louis community.

A member of the research team will review screening materials and contact potential participants by phone. This member of the research team will provide parent participants with information about the study and required elements of consent over the telephone prior to obtaining the parent's verbal consent to participate in the screening elements of the study (Initial Phone Screen as well as SCARED/MFQ). After obtaining verbal consent, a research assistant will administer the Initial Phone/Exclusion Screen to all potential participants. If a parent and child meet eligibility criteria for enrollment in the study based on their Initial Phone Screen, and parents indicate they wish to continue with the study, the research team will arrange an in-person assessment. On the day of the in-person assessment, a research assistant will provide ample time for the parents to read/review the consent form and will answer any questions the parent may have prior to signing.

2.d Randomization Method and Blinding

Subjects will be randomized to active vs. sham treatment on a 50/50 basis. The participants and the staff performing the pre- and post- treatment psychiatric interviews will remain blinded throughout the study. Study staff administering the treatment will be aware of the active vs. sham status of the participant, in order to deliver and monitor the appropriate cognitive training program.

2.e Risks and Benefits

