There are minimal risks associated with this study. Parents and children may feel uncomfortable or bored during the first assessment during the clinical interview. There is also a risk of breach or confidentiality. During the cognitive training, risks for child participants include boredom and very slight physical discomfort due to sitting and using a chin rest. MRI scans involve no major risks for subjects without implanted metal objects. Subjects are extensively screened before scanning and are not allowed to participate if they have any implanted metal objects. Additional minor potential risks of MRI are discomfort from being in a small space and lying still in one position for a long time. There are also loud noises made by the scanner but subjects will wear earphones to mask the sound.

The benefits to this study are that the treatment could potentially alleviate symptoms and distress in a participant. Also the participant is receiving a free diagnostic assessment, which typically is expensive and takes a long period of time to get an appointment.

2.f Early Withdrawal of Subjects

Subject participation in the study is completely voluntary and they can choose to withdraw at any time.

2.g When and How to Withdraw Subjects

If subjects meet exclusion criteria in their initial in office assessment, they will be withdrawn from the study. Subjects may also choose to withdraw from the study at anytime.

E3 Study Device

Cognitive Behavioral Training

3.a Description

The cognitive training program is designed by [name]. It is designed to lower activity in the VAN by reducing the influence of extraneous, salient stimuli, thereby reducing stimulus-driven attention and potentially anxiety.

To begin a trial, subjects fixate a central crosshair; 150 ms later, an arrow "cue" appears at the center of the screen and subjects are instructed to voluntarily direct their attention toward the location indicated by arrow. Following a random delay of 1, 2, or 3 seconds, subjects indicate whether a "target" (that always appears at the location indicated by the initial arrow cue).

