Active training: In between the presentation of the cue and target, three "distractor" boxes appear at irrelevant locations at random times. Subjects are instructed to ignore these boxes. It is the active ignoring of these boxes, while maintaining attention voluntarily at the cued location that is proposed to reduce subjects' stimulus-driven attention and reduce excessive VAN activity. **Sham training:** Subjects perform the same

number of trials, of the same task, with the exception that the "distractor" boxes never appear. Thus, subjects still have to voluntarily direct attention, but they do not get practice ignoring irrelevant distractors. Both subjects and clinical interviewers will be

blinded to active versus sham treatment. Subjects will be randomized to treatment arm.

3.b Treatment Regimen

Half of the subjects will be randomized to active cognitive training and half will be randomized to sham training. Children will participate in 8 total 30-minute training sessions, twice a week for 4 weeks.

3.c Method for Assigning Subjects to Treatment Groups

Subjects will be randomized to active vs. sham treatment on a 50/50 basis.

3.d Subject Compliance Monitoring

Subjects will be participating in the cognitive training program twice a week for four weeks in the presence of a trained research assistant.

3.e Blinding of Study Drug

Subjects will not be aware if they are participating in the active or sham treatment.

F Study Procedures

F1 Screening for Eligibility

Subjects will be screened over the phone standardized parent-report psychiatric instruments (Screen for Anxiety and Related Disorders, SCARED; and Mood and Feelings Questionnaire, MFQ).

F2 Visit 1

Child/Parent In-Office Assessment:

Parents will begin by completing Kiddie Schedule for Affective Disorders and Schizophrenia Present and Lifetime Edition (K-SADS-PL), the Pediatric Rating Scale, (PARS), and the Family Interview for Genetic Studies (FIGS) with trained research staff. These semi-structured interviews will be audio taped and will only be listened to by study staff. Parents will also complete additional questionnaires. The child will participate in a computer game that is designed to test various aspects of their attention.

The child will rest their chin on a chin rest and their eye movements will be recorded. There are three different versions of the game. In each version, the computer game involves looking at a central "+" sign and pressing a button when a target appears in

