either the center of the screen or the periphery. The child will also view different shapes and faces (happy, sad, angry, scared, and neutral) while engaged in the computer game. Following the game, the child will answer questionnaires (general questionnaire, SCARED, Childhood Depression Inventory (CDI), MFQ, and Pubertal Development Scale(PDS)) and participate in the child version of the K-SADS and PARS.

F3 Visit 2

Neuroimaging Visit:

MRI Simulation/Stillness Training: Child participants will complete a MRI training session to collect data on movement inhibition and prepare subjects for future MRI testing. Research indicates that an MRI simulation exercise prior to scanning increases the likelihood of a successful scan. Given that, an introduction to/explanation of the scanning procedure and a simulation exercise will be introduced at the conclusion of the child assessment. The child interviewer will engage the child in an MRI simulation. In this simulation, the child will practice lying still in a mock scanner environment. The child will practice lying still while listening to recorded MRI sounds and receiving visual feedback of their head movement. Feedback will be provided using motion tracking software, MoTrak 3D, connected to a video screen viewed from the scanner by the research subject. Subject movement and responsiveness to the training procedures will be recorded. Children will also be shown a video in which the scanning center is introduced and the scanning procedure is explained to the child. In the video, the child will see another child participating in the MRI procedure.

The NEUROIMAGING TRAINING could take place on the same day following the IN-PERSON ASSESSMENT, on the same day before the NEUROIMAGING VISIT, or on its own day, depending on the preference of the participant.

Before the MRI scan, parents will complete the MRI Safety checklist to ensure the child safety in the scanner and the child will complete a shortened version. The child will complete a 90 minute MRI scan before and after the cognitive training. We acquire a T1-weighted MP-RAGE, a T2 image, 4 five-minute "resting" functional scans, and 4 four-minute "task" functional scans. During the resting scans, the subjects with fixate a cross and during task blocks, subjects will complete the attention tasks. There will be no contrast used for this MRI scan.

F4 Visit 3-10

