The child will participate in 8 thirty minute training sessions, twice a week for four weeks. They will complete the cognitive training program that has been designed by [name].

On the day of sessions 2, 4, 6, and 8 subjects and parents complete the SCARED either in office or by a secure e-mail survey invitation via REDcap in order to assess anxiety over treatment. After session 8, subjects will be asked to rate tolerability of the training on a 5 point Likert scale.

F5 Visit 11

This visit will be after all 8 training sessions are completed and is identical to visit 1.

F6 Visit 12

This visit will be after all 8 training sessions and visit 11 are completed and is identical to visit 2.

Follow-up via Phone/Zoom

A member of the research team will explain that this is completely optional and will review the online survey process with the family over the phone or zoom. If the family agrees to participate, the research team member will e-mail a RedCap survey link that will start with the consent form. Researcher will walk participant through how to complete the surveys over the phone or zoom. Participants will have adequate time to review the consent document and there will be an e-mail address provided if the participant should have any questions. The participants e-signature through REdCap will have a time stamp. After the consent is signed, research staff will send an electronic copy of the signed consent document to the participant via e-mail.

G Statistical Plan

G1 Sample Size Determination and Power

Power analyses for two-tailed, two independent groups (active versus sham) comparisons were performed using G*Power 3.1. Based on prior work, we expect training to have a minimum effect size of 0.3 for changing symptoms of anxiety. Based on this effect size, we have 83% power to detect group differences in treatment effects (n=90, plus 10% failure). Power calculations are not computed for fMRI analyses because we have no effect size estimate; sample size is similar to other recent pilot studies.

G2 Interim Monitoring and Early Stopping

Subjects may withdraw from the study at any time. Each cognitive training session takes place in the lab. Study staff will converse with study subjects before and after each training session in order to assess for any adverse events.

G3 Analysis Plan / Statistical Methods

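### Adverse events are sought only by conversation with the child at training sessions, probably by staff who know the arm, and no enquiry is stated for parents or for Visits 11 and 12

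*Combined protocol and SAP*

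**What the plan says.** Section G2 holds the only adverse event procedure: "Study staff will converse with study subjects before and after each training session in order to assess for any adverse events". It does not say which staff do this, what they ask, or how answers are recorded. The instrument list in K2 has no adverse event form. G3 contains no harms analysis, and section J plans papers on the primary outcome and the neural effects only.

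On blinding, section 2.d says: "Study staff administering the treatment will be aware of the active vs. sham status of the participant". It also says: "The participants and the staff performing the pre- and post- treatment psychiatric interviews will remain blinded throughout the study". Section 3.d describes the sessions: "Subjects will be participating in the cognitive training program twice a week for four weeks in the presence of a trained research assistant".

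On procedures other than training, F3 says: "The child will complete a 90 minute MRI scan before and after the cognitive training". Section 2.e attaches named risks to the scan: "Additional minor potential risks of MRI are discomfort from being in a small space and lying still in one position for a long time". E1 describes the assessment tasks: "Children also complete 3 different computer games (taking between 60 and 90 minutes total". F5 and F6 make Visits 11 and 12 repeats of Visits 1 and 2, after all training is finished.

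Other data touch on harm without being called adverse event collection. F4 has child and parent complete the SCARED at sessions 2, 4, 6 and 8, and has the child rate tolerability of the training on one 5-point item after session 8. Visit 11 repeats the K-SADS and PARS with blinded interviewers.

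**The concern.** This is the first use of this training in anxious children. D2 reports no clinical data on it, and D1 offers a pilot in 4 healthy children. The harms record from this trial will therefore be the main direct evidence on tolerability, and its quality depends on how events are sought.

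Three features weaken it. First, a trainer who knows the arm may probe or record differently in active and sham children, and an open conversation gives nothing to hold the two arms to the same enquiry. Secondly, the enquiry is put to the subjects. E1 and F4 name caregivers or parents separately when they are meant, so parents are not included in G2. The children are as young as 7, and a reaction between sessions would often be seen first at home. C3 values the PARS for this kind of reason: "Because it includes multiple informants and is anchored by a clinician, it has high reliability and validity and is widely used". The same reasoning is not applied to harms. Thirdly, the last stated enquiry is the one after session 8, so complaints from the second scan and the repeat tasks have no stated route into the record.

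**Working it through.** The plan gives no rate, precision or sample size for harms, so there is no figure of its own to reproduce. The check is how much stated procedure time is followed by at least one adverse event enquiry.

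**Inputs**
- Training: 8 sessions of 30 minutes (3.b, F4): 8 × 30 = 240 minutes.
- MRI: 90 minutes at Visit 2 and again at Visit 12 (F3, F6): 2 × 90 = 180 minutes.
- Assessment tasks: 60 to 90 minutes at Visit 1 and again at Visit 11 (E1, F5): 120 to 180 minutes.
- Interviews: no duration stated.

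**Total timed exposure**
- With 60-minute tasks: 240 + 180 + 120 = 540 minutes.
- With 90-minute tasks: 240 + 180 + 180 = 600 minutes.

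**What the conversation can reach.** It is held at the start as well as the end of each session and covers any adverse event. Visits 1 and 2 come before session 1, so the first conversation can pick up complaints from them, though late. Intervals between sessions can be picked up at the next one. Only Visits 11 and 12 have no later conversation.

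**Share with no later enquiry** = (Visit 11 tasks + Visit 12 MRI) / total
- 60-minute tasks: (60 + 90)/540 = 150/540 = 27.8%.
- 90-minute tasks: (90 + 90)/600 = 180/600 = 30.0%.
- Training and MRI only: 90/(240 + 180) = 90/420 = 21.4%.

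**Sensitivity to interview time (assumed, since none is stated)**
- Interviews of 60 to 240 minutes at each assessment visit, added to training, MRI and tasks: (150 + 60)/(540 + 120) = 210/660 = 31.8%, up to (180 + 240)/(600 + 480) = 420/1080 = 38.9%.
- Only the exposures to which 2.e attaches a risk (training, both scans and the first-assessment interview, taken as 0 to 240 minutes): 90/420 = 21.4%, down to 90/660 = 13.6%.

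**Time outside training sessions, for contrast**
- (180 + 120)/540 = 55.6%, up to (180 + 180)/600 = 60.0%.
- Training and MRI only: 180/420 = 42.9%.

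This last measure is not time without enquiry, because it counts Visits 1 and 2 as missed.

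**Who asks.** G2 says only study staff. Section 2.d makes those who administer training unblinded, and 3.d puts a research assistant in every session. No text gives the task to blinded staff. An unblinded enquirer is the natural reading, but it is an inference.

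**The case against.** The case for leaving this alone is respectable. The named risks are mild: boredom, fatigue, slight stiffness, and discomfort in the scanner. D2 cites meta-analyses of similar programs with no known adverse events. The child who reports is blinded. The tolerability item, the child and parent SCARED, and the blinded Visit 11 interviews would show poor acceptance or worsening anxiety or mood, including after session 8. This stands, and it keeps the point small. It does not remove it: one 5-point item on training cannot identify an event or cover a scan, and the SCARED, K-SADS and PARS measure symptoms or diagnosis, not other complaints.

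Four stronger readings are tempting, and the documents do not support them.
- A reader might infer that more than half of the exposure is never asked about. That takes time outside training as time without enquiry. The conversation before session 1 can reach Visits 1 and 2, and no measure of time without a later enquiry computed above reaches half.
- A reader might infer that the plan makes an unblinded comparison of harms between arms. G3 plans no such comparison. The gap is that none is specified, and that a later one would rest on elicitation probably done by staff who know the arm.
- A reader might infer that these conversations carry expectancy into the SCARED. This is plausible but not shown. The trainer is unblinded and present whether or not adverse events are discussed, and F4 allows the SCARED to be completed by e-mailed survey.
- A reader might quote upper bounds on event rates from zero events in the pilot or in one arm. Those bounds depend only on the number of children and do not measure this defect.

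**Conclusion.** The point holds as a modest weakness in harms collection. Three gaps are plain in the text: no adverse event question for parents, none at Visits 11 and 12, and no harms summary in G3. That the enquirer knows the arm is probable, not stated.

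The size is about 28% to 30% of timed procedure exposure without a later enquiry, or 21% if only training and MRI are counted. This rests on the stated durations, on Visits 11 and 12 taking place as scheduled after session 8, and on giving the first pre-session conversation full credit for Visits 1 and 2. Untimed interviews could move the share in either direction: across the assumptions shown, the range is 13.6% to 38.9%. Minutes are a rough measure of opportunity for complaints, not of risk.

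Efficacy conclusions are not affected. What suffers is the ability to say that a tolerability difference between arms, or its absence, is not a product of how the question was put.

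**What to change.** Replace the conversation in G2 with one short fixed list covering the risks named in D3 and 2.e, plus one open question, worded identically in both arms and recorded on a form.
- **Child:** ask at each session, and after each scan (Visits 2 and 12).
- **Parent:** add the same items to the SCARED/REDCap survey at sessions 2, 4, 6 and 8, placed after the SCARED items.
- **Visit 11:** collect the items from child and parent on a self-completed form, or through the blinded interviewer only after the K-SADS and PARS are scored. The order matters. Only active children see the distractor boxes (3.a), so a child describing a complaint could reveal the arm to the rater before the PARS is fixed.
- **G3:** state that counts will be reported by arm descriptively, with the Visit 11 report used for any comparison of arms. Show the session reports alongside, since children who withdraw will not reach Visit 11.
- **G2:** state which staff ask.

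The cost is protocol wording, one form and a few survey items. No new visits or staff are needed. The downside is a few minutes per visit and more minor complaints recorded in both arms, as prompted lists tend to produce.

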The primary outcome will be reduction in symptoms of anxiety as measured by the SCARED in study Phase 2. Total SCARED scores at sessions 2, 4, 6, and 8 will be subtracted from the baseline SCARED score, yielding a delta SCARED score for each

visit. These data will be analyzed with a mixed random effects repeated-measures model. In this model, time, treatment (active versus sham), and time x treatment interaction are fixed effects; baseline SCARED scores and subject within treatment are random effects; and delta SCARED scores are the dependent variable. Our hypothesis predicts a significant time x treatment interaction, with a greater decrease in anxiety from pre- to post- training in the active relative to the sham group. Secondary outcomes will include symptoms of anxiety on the PARS and diagnostic status.

We will test whether active versus sham training significantly reduces symptoms in children with anxiety disorders. The primary outcome will be reduction in symptoms of anxiety as measured by the PARS. We will perform a 2 x 2 ANOVA with treatment arm (active versus sham) and time (pre- versus post-training) as effects of interest.

G4 Missing Outcome Data

We will use an intention-to-treat analysis and carry the last observation forward. Because this is a pilot study, we will also compare active versus sham treatment among completers in a follow-up analysis.

G5 Unblinding Procedures

The principal investigator will be made aware of each subject's assignment after that subject has completed all study procedures including post-treatment psychiatric assessment.

H Data Handling and Record Keeping

H1 Confidentiality and Security

Telephone conversations about the study, the consent process, and all portions of the study will take place in a private office. All subjects will be marked with a random identification number so names will not be recorded on any of the data. All data will be stored in locked filing cabinets and on password protected computers. Also, only the research team will have access to study information. Participants can refuse to answer any questions and withdraw from the study at any time.

H2 Training

All current study staff have extensive experience in study procedures, based on similar prior studies performed in the lab. Any new personnel will be trained by current study staff.

H3 Case Report Forms and Source Documents

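### G3 names SCARED and then PARS as the primary outcome, under different models, with no alpha, testing order or multiplicity rule to say which one decides the trial

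*Combined protocol and SAP*

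**What the plan says.** **C1 (Primary Aim):** "The primary outcome will be reduction in symptoms of anxiety as measured by the Pediatric Rating Scale (PARS").

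**C3** gives a rationale for PARS only: "Because it includes multiple informants and is anchored by a clinician, it has high reliability and validity and is widely used".

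**G3, first paragraph:** "The primary outcome will be reduction in symptoms of anxiety as measured by the SCARED in study Phase 2". Change from baseline at sessions 2, 4, 6 and 8 goes into a repeated-measures mixed model. The deciding term is named: "Our hypothesis predicts a significant time x treatment interaction". The paragraph closes by placing PARS, with diagnostic status, among the secondary outcomes.

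**G3, second paragraph:** PARS is the primary outcome, analysed by a 2 x 2 ANOVA with arm and time (before and after training) as the effects of interest.

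**F4** describes the session SCARED, completed in the office or "via REDcap in order to assess anxiety over treatment". **F2 and F5** place PARS at Visit 1 and at Visit 11, which repeats Visit 1.

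**G1** refers to a two-tailed comparison of two independent groups and says "we expect training to have a minimum effect size of 0.3 for changing symptoms of anxiety". It reports 83% power with n=90 plus 10% failure. It names no scale, no effect-size metric and no alpha.

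**The concern.** Within one section, PARS is both secondary and primary. The two candidate analyses differ in scale, time points, model and data structure, so they can disagree. If they do, an analyst following the first paragraph of G3 would report SCARED as the trial's result, and one following the second paragraph would report PARS. Both could cite the plan.

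Two things could have separated the claims and do not. The reference to a study Phase 2 might have limited the SCARED statement to part of the trial, but no phases are defined; E1 lists only assessments and training. A co-primary design might have been meant, but nothing says so, and calling PARS secondary rules it out.

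What is at stake is the meaning of the main efficacy claim. Section J plans manuscripts on a primary outcome in the singular, and the plan does not fix which outcome that is.

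**Working it through.** **1. The passages side by side**

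| Place | Primary outcome | Status of PARS | Analysis |
|---|---|---|---|
| C1 | PARS | primary | not given |
| C3 | (rationale for PARS only) | - | - |
| G3, first paragraph | SCARED | secondary | mixed model, sessions 2, 4, 6, 8 |
| G3, second paragraph | PARS | primary | 2 x 2 ANOVA, before/after |
| G1 | symptoms of anxiety, no scale | - | two-group, two-tailed |

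Three places lean to PARS and one states the reverse order. This needs no calculation.

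**2. Type I error if either test could be claimed**

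Assumptions, none of them in the documents: two-sided 5% per test, and success on either test suffices.

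- Independent tests: 1 - 0.95² = 0.0975.
- Any dependence (Bonferroni bound): at most 0.05 + 0.05 = 0.10.
- Correlated normal test statistics: 1 - P(|Z1| < 1.96, |Z2| < 1.96). At an assumed correlation of 0.8 this is 0.0781.

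The correlation between the two test statistics cannot be read from the documents, so the usable statement is above 5% and at most 10%. With a single primary outcome it is 5%.

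**3. G1's 83%**

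Inputs from G1: effect size 0.3, n=90, 10% failure, two-tailed. Allocation is 1:1 (2.d). Assumed: alpha 5%.

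The two-sample t test with 45 per arm has noncentrality d/√(1/45 + 1/45) = d × 4.743, with 88 df.

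- 0.3 as a standardised mean difference d: 0.3 × 4.743 = 1.42; power 29.1%.
- 0.3 as Cohen's f, so d = 2f = 0.6: 0.6 × 4.743 = 2.85; power 80.4%.
- 0.3 as a correlation r (Fisher z): atanh(0.3) × √87 = 0.3095 × 9.327 = 2.89; 2.89 - 1.96 = 0.93; power 82.3%.

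The phrase about 10% failure can also be read in more than one way:

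| Analysed N | d = 0.3 | f = 0.3 | r = 0.3 |
|---|---|---|---|
| 81 (90 less 10%) | 26.6% | 76.0% | 78.0% |
| 90 | 29.1% | 80.4% | 82.3% |
| 99 (90 × 1.1) | 31.5% | 84.0% | 85.8% |
| 100 (90 / 0.9) | 31.8% | 84.4% | 86.2% |

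The stated 83% is not reproduced if 0.3 is d. It is approached within about 1 to 1.5 points if 0.3 is f with N of 99 to 100, or r with N of 90. The documents do not say which was meant.

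**The case against.** The strongest reply is that the documents already resolve the matter. C1 is the statement of the primary aim, C3 defends only PARS, the second paragraph of G3 agrees, and F4 presents the session SCARED as tracking anxiety during treatment. On that view the first paragraph is a leftover. The lean is real and settles which way to repair the text. It does not remove the contradiction, because the conflicting order stands in the section an analyst will follow.

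The pilot label in C1 and G4 does not dispose of it either: the aim in C1 is "Test the efficacy of a novel computer-based cognitive training program".

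Four stronger readings are tempting and are not supported:

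- **That the 83% power is wrong.** Showing only the d reading (29%) would suggest this. The f and r readings come close to 83%, so the figure is unclear rather than refuted.
- **That the PARS analysis has no deciding test.** The second paragraph does not name the interaction, but an arm-by-pre/post ANOVA with a hypothesis framed relative to sham (A2) implies it. Naming it is a clarification.
- **That the trial's error rate is close to 10%.** The plan states no either-test rule and no alpha, and the correlation is unknown. The figures show what the ambiguity permits.
- **That the primary outcome was chosen after seeing results.** G5 gives the principal investigator each assignment once that subject finishes, and this version (12/10/2020) postdates the planned study period of January 2018 through June 2019. Neither fact shows that outcomes were compared by arm. They only justify asking for a statement.

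**Conclusion.** The concern holds as a contradiction in the current text of G3, and it should be resolved before any result is reported as primary. The finding itself rests on wording alone. Its size, as type I error, lies above 5% and is at most 10%, on the assumptions that each test is run at two-sided 5%, that either could be claimed, and that the two statistics are not perfectly correlated. Fixing the primary outcome also brings in G1, because its power statement cannot be assigned to PARS or SCARED as written. Depending on how 0.3 is read, power with 90 analysed runs from 29% to 82% at an assumed two-sided 5%. That range measures the ambiguity and does not show the sample size to be inadequate.

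**What to change.** Make PARS, Visit 1 to Visit 11, rated by the blinded interviewer, the single primary outcome. C1 and C3 then stand unchanged, and the assessor is already covered by 2.d: "The participants and the staff performing the pre- and post- treatment psychiatric interviews will remain blinded throughout the study".

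- **G3, first paragraph:** relabel the SCARED trajectory as secondary, and delete the reference to a study Phase 2. In the secondary-outcomes sentence, remove only the mention of PARS, so that diagnostic status stays. While this paragraph is open, say whose SCARED report is scored, since F4 collects it from both subjects and parents and G3 does not choose.
- **G3, second paragraph:** name the treatment arm x time interaction as the deciding test, at a stated two-sided alpha.
- **G1:** state the scale and effect-size metric behind 0.3 and whether 90 is before or after the 10% failure, then confirm or restate the power for the PARS interaction test.
- **Amendment:** date it and state whether outcomes had already been compared by arm. If they had, label the choice post hoc and report both the SCARED and the PARS result.

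The cost is one amendment and a power calculation, with no new data. SCARED loses its primary label, and the restated power may be below 83%. If outcomes have already been compared by arm, the amendment can disclose the choice but cannot restore error control.
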